3.2 Design of the clinical trial

This is a Phase I, multi-centre, dose escalation study (any solid tumour) with an expansion cohort (NSCLC).

3.2.1 Dose escalation

The final number of patients recruited to this phase will depend on the number of dose escalations required to reach the RP2D.

In the dose escalation stage of the study, the Sponsor reserves the right to investigate alternative doses of vandetanib and selumetinib in response to emerging safety data. Recruitment into cohorts will follow a “rolling-six” design. Dose assignment for each cohort will be carried out, using all available data, by the Sponsor in conjunction with the CI and PI(s). Cohorts of three to six patients will be entered at each dose level.

If one out of three patients experience a DLT (as defined in Section 3.1.1, up to six patients will be treated at that dose).

If one out of up to six patients experience a DLT, dose escalation will continue.

If two out of up to six (i.e. between two and six) patients experience a DLT dose escalation will stop and this dose will be defined as the maximum administered dose (MAD). At least three more patients will be treated at a dose below the MAD to define the MTD.

Each of the cohorts will assess vandetanib in combination with selumetinib. Selumetinib will initially be administered at three dose levels, 25, 50 and 75 mg (oral, twice daily).

The first three cohorts will initially investigate combining vandetanib (100mg, once daily) with increasing doses of selumetinib as follows:

Study cohort	Vandetanib	Selumetinib
Cohort 1	100 mg po od	25 mg po bd
Cohort 2	100 mg po od	50 mg po bd
Cohort 3	100 mg po od	75 mg po bd

Should MTD not be achieved on completion of Cohort 3, recruitment will continue into additional cohorts investigating alternative doses of selumetinib and vandetanib in combination.

The dosing regimen for each new cohort will be communicated and confirmed to clinical sites following the dose review meetings on completion of each cohort.

Cycle 1 will consist of 42 days. This includes the 14 days of vandetanib alone plus the 28 days of combination treatment.

Subsequent cycles will be of 28 days in length and consist of continuous treatment with vandetanib and selumetinib at steady state. There is no planned interval between cycles. Patients may continue to receive the combination therapy in the absence of disease progression or unacceptable toxicity (please see Section 5.6).

Pharmacokinetic parameters will also be measured pre and post treatment with single agent vandetanib and following combination treatment with selumetinib.

At the end of the dose escalation phase, safety data including a listing of all AEs will be collated and reviewed against the study objectives and endpoints. The decision to proceed to the expansion cohort will be made by the Sponsor following review of the data by the Sponsor (to include review by the Protocol and Safety Review Board), Chief Investigator and Principal Investigators. This decision will be communicated to all investigator sites by the Sponsor.

3.2.2 Expansion cohort

Once the RP2D of the combination has been determined, a further 30 NSCLC patients will be treated at this dose level.

All patients will continue to be assessed for safety and tolerability of the combination treatment. All patients will be imaged and will also be asked to consider additional consent to

CRUKD/11/001 Protocol version 13.0 FINAL 26Jan2018

EudraCT number: 2011-000627-33

© Cancer Research UK

an optional biopsy sampling schedule. It is expected that a minimum of 20 patients will complete the full imaging schedule and a minimum of 10 patients will consent to be biopsied. Patients who undergo the additional biopsies may also complete the full imaging schedule if further evaluable lesions are identified.

Imaging will be performed to measure tumour vascularisation and metabolism using FDG-PET [REDACTED] These functional imaging assessments will take place pre and post treatment with single agent vandetanib and following combination treatment with selumetinib. [REDACTED]
[REDACTED]
[REDACTED]

Progression free survival will be assessed at 12 weeks and one-year survival will also be recorded.

3.2.3 Study duration

Following completion of recruitment to the dose escalation phase, the data will undergo review and assessment by the Sponsor. The Sponsor will confirm the decision to proceed to the expansion cohort.

The recruitment period of the dose escalation phase could increase pending the addition of further cohorts to investigate alternate doses of the study drug combination.

Patients can continue on study treatment on observation of SD, PR or CR therefore time on study for patients cannot be defined. Patients may continue to receive the combination therapy in the absence of disease progression or unacceptable toxicity. If the patient has not progressed after 6 cycles, they may be treated for further cycles after a formal written request has been made to and written approval received from the Sponsor.

4 PATIENT SELECTION

4.1 Eligibility criteria

The patient must fulfil the eligibility criteria (listed in Sections 4.1.1 and 4.1.2).

4.1.1 Inclusion criteria

1. **(Dose escalation cohorts)** Histologically or cytologically proven solid tumour for which no conventional therapy exists or is declined by the patient
2. **(Expansion cohort only)** Histologically or cytologically confirmed NSCLC patients only, for which no conventional therapy exists or is declined by the patient.
 - If only cytologically confirmed, baseline biopsy is mandatory for a patient to be eligible.
 - For NSCLC patients to be eligible for the expansion cohort they must have received:
 - One prior line of chemotherapy and/or
 - Previous platinum based chemotherapy and/or
 - At least one previous EGFR inhibitor
3. **(Expansion cohort only)** Measurable disease according to RECIST criteria Version 1.1
4. Life expectancy of at least 12 weeks
5. World Health Organisation (WHO) performance status of 0-1 (Appendix 1)
6. Baseline LVEF $\geq 50\%$
7. Haematological and biochemical indices within the ranges shown below. These measurements must be performed within one week (Day -7 to Day -1) before the patient goes on study.

Laboratory Test	Value required
Haemoglobin (Hb)	≥ 9.0 g/dL
Absolute neutrophil count	$\geq 1.5 \times 10^9$ /L
Platelet count	$\geq 100 \times 10^9$ /L
Normal serum calcium (adjusted)*	2.15-2.55 mmol/L
Normal serum magnesium*	0.60-1.0 mmol/L
Normal serum potassium	≥ 4.0 mmol/L
Either: Serum bilirubin	$\leq 1.5 \times$ upper limit of normal (ULN) This does not apply to patients with Gilbert's disease.
Or: Alanine amino-transferase (ALT) or aspartate amino-transferase (AST) and alkaline phosphatase (ALP)	$\leq 2.5 \times$ ULN unless raised due to liver metastases in which case up to 5 x ULN is permissible
Either: Calculated creatinine clearance (using the Wright or C&G formula)	> 50 mL/min
Or: Isotope clearance measurement**	≥ 50 mL/min (uncorrected)
INR or aPTT***	$< 1.5 \times$ ULN

*or normal range according to the local laboratory

** Isotope clearance result to be used to confirm eligibility if calculated C&G/Wright method results in GFR of $= 50$ mL/min.

*** Therapeutic INR values (2.0-3.0) are acceptable to confirm eligibility for patients who are taking concomitant warfarin.

8. 18 years or over

9. Ability to swallow and retain oral medications.
10. Written (signed and dated) informed consent and be capable of co-operating with treatment, and follow-up

4.1.2 Exclusion criteria:

1. Radiotherapy (except for palliative reasons), endocrine therapy, immunotherapy or chemotherapy during the previous 4 weeks (6 weeks for investigational medicinal products) before treatment.
2. Patients who have been withdrawn from treatment with agents that target EGFR because of unacceptable toxicity (prior treatment with these agents is allowed) and those patients who have had an EGFR dose reduction by 50% or more (dose modifications as per standard clinical practice is allowable and is not considered a reduction e.g. afatinib administration).
3. Expansion cohort only: Prior treatment with any agent that targets MEK or VEGFR or VEGF
4. Any prior exposure to RAS or RAF inhibitors
5. Ongoing toxic manifestations of previous treatments. Exceptions to this are alopecia or certain Grade 2 toxicities, which in the opinion of the Investigator and the Centre for Drug Development (CDD) should not exclude the patient.
6. Symptomatic brain metastases (patients must be stable for >3 months post RT treatment) or spinal cord compression.
7. Patients with interstitial lung disease.
8. Pregnant or lactating women are excluded. Female patients with the ability to become pregnant who have a negative serum or urine pregnancy test before enrolment and agree to use two of the following three highly effective forms of combined contraception (oral, injected or implanted hormonal contraception and condom, have a intra-uterine device and condom, diaphragm with spermicidal gel and condom) for four weeks before entering the trial, during the trial and for six months afterwards are considered eligible.
9. Male patients with partners of child-bearing potential (unless they agree to take measures not to father children by using one form of highly effective contraception [condom plus spermicide] during the trial and for six months afterwards). Men with pregnant or lactating partners should be advised to use barrier method contraception (e.g. condom plus spermicidal gel) to prevent exposure to the foetus or neonate.
10. Major surgery from which the patient has not yet recovered.
11. At high medical risk because of non-malignant systemic disease including active uncontrolled infection.
12. Known to be serologically positive for Hepatitis B, Hepatitis C or Human Immunodeficiency Virus (HIV).
13. Cardiac conditions as follows:
 - Clinically significant cardiovascular event within 3 months prior to entry to include:
 - Myocardial infarction
 - Angina requiring use of nitrates more than once weekly
 - Superior vena cava syndrome

- Class II/III/IV cardiac disease (New York Heart Association [NYHA]) (Appendix 4)
- Presence of cardiac disease that in the opinion of the Investigator increases the risk of ventricular arrhythmia.
- History of arrhythmia which is symptomatic or requires treatment (CTCAE 4.02), symptomatic or uncontrolled atrial fibrillation despite treatment or asymptomatic sustained ventricular tachycardia. Patients with atrial fibrillation controlled by medication are permitted.
- Uncontrolled hypertension (BP > 160/100 despite optimal therapy)
- Prior or current cardiomyopathy
- Atrial fibrillation with heart rate >100 bpm
- QTcB (Bazett's formula) > 450 msec on screening ECG (Note: If a patient has a QTcB interval \geq 450 msec on screening ECG, the screen ECG may be repeated twice [at least 24 hours apart]. The average QTcB from the three screening ECGs must be < 450 msec in order for the subject to be eligible for the study.)
- History of congenital long QT syndrome
- History of Torsade de Pointes (or any concurrent medication with a known risk of inducing Torsades de Pointes. See Appendix 16.8)

14. Concomitant medications that are potent inducers of CYP3A4 function i.e. rifampicin, rifabutin, phenytoin, carbamazepine, Phenobarbital and St John's Wort.

15. Any other condition which in the Investigator's opinion would not make the patient a good candidate for the clinical trial (e.g. evidence of severe or uncontrolled systemic disease or concurrent condition or that may affect ability to absorb oral agents).

16. Current malignancies of other types, with the exception of adequately treated cone-biopsied in situ carcinoma of the cervix uteri and basal or squamous cell carcinoma of the skin. Cancer survivors, who have undergone potentially curative therapy for a prior malignancy, have no evidence of that disease for five years or more and are deemed at negligible risk for recurrence, are eligible for the trial.

17. If a participant plans to participate in another interventional clinical study, whilst taking part in this Phase I study. Participation in an observational study would be acceptable.

18. Ophthalmological conditions as follows:

- a. Current or past history of retinal pigment epithelial detachment (RPED)/central serous retinopathy (CSR) or retinal vein occlusion.
- b. Intraocular pressure (IOP) > 21 mmHg or uncontrolled glaucoma (irrespective of IOP).

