2.2.1.4 Clinical Pharmacokinetics

The PK of vandetanib is linear. The steady state exposure is reached at day 28 with a once-daily dosing. The absorption is slow with a median time to maximum plasma concentration (t_{max}) of 4 to 10 hours. The slow clearance (total plasma clearance after an oral dose (CL/f) of 11 L/h) and the large volume of distribution (3000 L) give a long terminal half-life (t_{1/2}) of about 10 to 19 days. Vandetanib is eliminated both in the faeces and in urine. Therefore, in patients with mild and moderate renal impairment the exposure is increased by about 1.5-fold and by 2-fold in patients with severe renal impairment. Hepatic impairment or food has no effect on exposure. In healthy volunteers, the CYP3A4 inhibitor, itraconazole did not modify the exposure to vandetanib but the CYP3A4 inducer rifampicin significantly reduced by about 40% the exposure to vandetanib.

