4.2 Patient enrolment

All patients who provide informed consent must be registered in the electronic data capture (EDC) system including any screen failures. The screening number will be automatically allocated during the process.

Before enrolling the patient in the trial, the Investigator or designated representative must determine the eligibility of the patient. Please ensure that CDD are notified of any eligibility concerns at least four working days before treatment is planned.

CONFIDENTIAL

Eligible patients must be enrolled in the EDC system before they start treatment with vandetanib. If the patient is eligible the patient number will be automatically allocated during the enrolment process.

Dose level allocation will be confirmed to the Investigator (and team as applicable) by the CDD following patient enrolment.

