5.4 Dose modifications

5.4.1 Dose interruptions

In the event of drug related toxicity, drug administration must be withheld (except for skin, fatigue, nausea, myalgia or arthralgia, unless these specific toxicities do not respond to supportive measures) until Grade 1 or below or until the patient meets the eligibility criteria parameters.

- On observation of a Grade 2 cardiac toxicity (any causality), both vandetanib and selumetinib should be stopped until resolution.
- On observation of G3 diarrhoea, if this does not resolve within 48 hours, both vandetanib and selumetinib should be stopped until resolution (i.e. until Grade 0 or 1 or until the patient meets the eligibility criteria parameters).
- On observation of non-specific respiratory signs and symptoms, where infectious, neoplastic, and other causes are unlikely or have been excluded and a diagnosis of interstitial lung disease (ILD) is likely or confirmed, both IMPs should be interrupted.

Patients must meet eligibility criteria parameters prior to each cycle and following a treatment interruption if the intention is to re-treat.

The maximum unscheduled dose interruption period is two weeks. Patients failing to recover to NCI CTCAE Grade 1 or less after two weeks will be withdrawn from the study.

There are overlapping toxicities associated with both vandetanib and selumetinib. Therefore it may not be clear which agent is responsible for any observed toxicity. If this is the case then administration of both drugs must be stopped at the same time until resolution to the above criteria.

Vandetanib administration should not be interrupted if possible; the aim is to maintain vandetanib to reduce the requirement to repeat the 'loading' phase of vandetanib administration. Therefore on observation of a Grade 2 drug related toxicity, selumetinib alone can be stopped (vandetanib can continue as a single agent administration). The patient should be closely monitored (whilst on vandetanib alone) to ensure the toxicity resolves to Grade 1 or less within 24 hours. If toxicity continues at same grade or increases within 24 hours then vandetanib should also be stopped.

To note: selumetinib should not be given as a single agent.

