5.9 Precautions for treatment

- a) Electrolytes to include serum magnesium and potassium must be maintained within normal limits (potassium MUST be maintained at > 4.0mmol/L).

Monitoring to occur weekly for Cycles 1 and 2 then prior to Day 1 of subsequent cycles.

- b) Patients should avoid excessive sun exposure and use adequate sun screen protection (SPF 50) if sun exposure is anticipated.
- c) Patients should be informed to notify their study doctor or nurse if they experience any visual disturbances or ocular pain.
- d) Selumetinib capsules contain D- α - Tocopheryl polyethylene glycol 1000 succinate (TPGS, a water-soluble form of vitamin E) as an excipient. The maximum daily dose of vitamin E that a study patient may receive from selumetinib is approximately 261.6mg/day. Therefore:

Patients should not take vitamin E supplements or multivitamin supplements which provide a total daily dose in excess of 100% of the recommended daily allowance for vitamin E. High doses of vitamin E have been reported to cause bleeding and interrupt blood coagulation processes.

- e) Interstitial lung disease (ILD) or pneumonitis has been observed with vandetanib, and deaths have been reported. Cases of ILD have also been observed with selumetinib when administered in combination with other agents, including docetaxel. A diagnosis of ILD should be considered in patients presenting with non-specific respiratory signs and symptoms such as hypoxia, pleural effusion, cough, or dyspnoea, and in whom infectious, neoplastic, and other causes have been excluded by means of appropriate investigations.
- f) Selumetinib should be administered with caution in patients who are also receiving concomitant coumarin anticoagulant medications e.g. warfarin. These patients should have their INR monitored/anticoagulant assessments conducted more frequently and the dose of the anticoagulant should be adjusted accordingly.
- g) Patients should avoid medications that are known to either induce or inhibit the activity of hepatic microsomal isoenzymes CYP1A2, CYP2C19 and CYP3A4, as this may interfere with the metabolism of selumetinib. Please see link to Flockhart list which provides a complete list of inhibitors/inducers
<http://medicine.iupui.edu/clinpharm/ddis/>.

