7.1.4 Evaluations within one week (seven days)

Dose escalation and expansion cohort

The following must be performed **within one week before** the patient receives the first dose:

- Complete physical examination;
- Height, weight, WHO performance status, temperature, blood pressure (BP sitting) and pulse rate;
- Electrocardiogram (ECG): Three to be performed within 5-10 minutes of one another;
- Echocardiogram (ECHO) / Multi gated acquisition scan (MUGA) (maintain one method at each site);

- Laboratory tests (blood/ urine samples) to confirm eligibility.
 - Haematology – haemoglobin (Hb), white blood cells (WBC) with differential count (neutrophils and lymphocytes), reticulocytes and platelets
 - Biochemistry – sodium, potassium, adjusted calcium, phosphate, urea, creatinine, total protein, albumin, bilirubin, alkaline phosphatase (alk phos), alanine aminotransferase (ALT), aspartate aminotransferase (AST), serum magnesium, creatine phosphokinase (CPK)
 - Urinalysis – glucose, protein and blood
 - Blood clotting measurements – INR or aPTT
- GFR assessment (calculated) using Wright or Cockcroft and Gault formula to be performed.
 - Isotope clearance result to be used to confirm eligibility if calculated C&G/Wright method results in GFR which equals 50 mL/min. Confirmatory Isotope clearance result in these cases must be \geq 50 mL/min.
 - GFR assessments as clinically indicated throughout study period (calculated C&G/Wright formula and/or Isotope clearance measurement as applicable).

Expansion cohort (Cycle 1) only:

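### Inclusion criterion 7 makes the bilirubin limit and the transaminase/ALP limit alternatives, so a patient who fails one of them still meets the criterion

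*Protocol*

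**What the plan says.** Criterion 7 in Protocol 4.1.1 asks for "Haematological and biochemical indices within the ranges shown below" and then gives a table. Two rows concern the liver:

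- *Either*: serum bilirubin at most 1.5 x ULN, with Gilbert's disease exempt.
- The alternative row, "Or: Alanine amino-transferase (ALT) or aspartate amino-transferase (AST) and alkaline phosphatase (ALP", with a limit of 2.5 x ULN, rising to 5 x ULN where liver metastases are the cause.

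The renal rows just below use the same *Either*/*Or* pair for calculated creatinine clearance and isotope clearance.

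The screening panel in Section 7.1.4 measures all four liver tests: "bilirubin, alkaline phosphatase (alk phos), alanine aminotransferase (ALT), aspartate aminotransferase (AST), serum magnesium" is part of its biochemistry list. Section 5.4.1 uses the entry limits again on treatment: "Patients must meet eligibility criteria parameters prior to each cycle and following a treatment interruption if the intention is to re-treat".

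**The concern.** In the renal rows the two entries are two ways of measuring one quantity, so one acceptable result is enough. Bilirubin and the enzymes are different quantities, and a normal value of one says nothing about how far the other is out of range. Joined as alternatives, each limit stops binding once the other is met.

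At stake is hepatic safety at entry to what Section 5.1.2 describes as the first human use of this combination. Section 2.2.2.4 reports a trend to raised transaminases with twice-daily selumetinib, which is the starting schedule. Section 3.1.1 counts related Grade 3 or 4 biochemical events as dose-limiting, and two such toxicities in up to six patients stop escalation (Section 3.2.1). Abnormal liver values at baseline could therefore also complicate attribution in small cohorts.

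**Working it through.** The protocol states no figure to reproduce here, so the check is one of logic.

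**Inputs (Protocol 4.1.1, criterion 7).** B = bilirubin at most 1.5 x ULN. E = ALT or AST, and ALP, at most 2.5 x ULN (5 x ULN with liver metastases).

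**Step 1. Truth table.**

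| B met | E met | As written (B or E) | Both required (B and E) |
|---|---|---|---|
| yes | yes | qualifies | qualifies |
| yes | no | qualifies | fails |
| no | yes | qualifies | fails |
| no | no | fails | fails |

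As written, 3 of 4 combinations qualify. With both required, 1 of 4 does. The two rows that change are the patients who fail exactly one limit.

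**Step 2. Illustrative patients** (assumed values in multiples of ULN, no Gilbert's disease).

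- Patient 1: bilirubin 1, ALT 10, AST 10, ALP 1. The transaminases are 10/2.5 = 4 times the ordinary limit and 10/5 = 2 times the liver-metastasis limit. The patient qualifies as written and fails if both limits are required, with or without liver metastases.
- Patient 2: bilirubin 4, ALT, AST and ALP 1. Bilirubin is 4/1.5 = 2.67 times its limit. The patient qualifies as written and fails if both limits are required.
- Patient 3: bilirubin 1, ALT 10, AST 2, ALP 1. The patient qualifies as written. If both limits are required but one transaminase in range is enough, the patient still qualifies, because AST 2 is below 2.5. This case bears only on the secondary question of what *ALT or AST* means.

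**Step 3. Is there another hepatic limit for entry?** The rest of the eligibility text offers these:

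- Criterion 7 itself: INR or aPTT below 1.5 x ULN, an indirect measure.
- Exclusion 5: ongoing toxicity of earlier treatment, with an exception for certain Grade 2 toxicities. It covers only abnormalities caused by treatment.
- Exclusion 11: high medical risk from non-malignant disease. Exclusion 12: known hepatitis B, hepatitis C or HIV. Exclusion 15: investigator's opinion.
- Section 4.2: "Please ensure that CDD are notified of any eligibility concerns at least four working days before treatment is planned". This depends on someone seeing a concern, which a criterion recorded as met may not raise.
- Section 5.9: a numeric contraindication for GFR, but none for liver function.

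None of these limits bilirubin, transaminases or ALP by value.

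**Step 4. Reach beyond entry.** Section 5.4.1 lets treatment resume at Grade 1 or below, or when the eligibility parameters are met. As written, an isolated breach of one liver limit already meets those parameters, so that route puts no check on it. The Grade 1 conditions in Section 5.4.2.1 and the two-week withdrawal rule in 5.4.1 partly offset this.

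**The case against.** The strongest reply is that the intent is recoverable. The lead-in speaks of indices within the listed ranges, all four tests are taken to confirm eligibility, and few investigators would enter a patient with ALT at 10 x ULN. This stands as far as it goes. It looks like a drafting slip, and meeting criterion 7 does not compel entry. A reader might infer that such patients would in practice be enrolled at any level of abnormality. The documents do not support that, given the backstops above and the performance-status and life-expectancy criteria. But the table's own connector states alternatives and means exactly that in the renal rows, and Section 14.1 allows no waivers of eligibility criteria, so the wording needs to be right.

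Two further inferences go too far:

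- **That both ALT and AST were meant to be in range.** The phrase may simply mean whichever transaminase the site uses. Requiring both would be a stricter criterion, not evident intent.
- **That raised liver tests are shown to alter drug exposure.** For vandetanib, Section 2.2.1.4 says "Hepatic impairment or food has no effect on exposure". For selumetinib, the nearest text is the Section 5.9 precaution about "hepatic microsomal isoenzymes CYP1A2, CYP2C19 and CYP3A4, as this may interfere with the metabolism of selumetinib". That concerns co-medications which induce or inhibit the enzymes, and says nothing about hepatic impairment.

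Section 2.2.2.4 adds that most transaminase rises stayed within normal limits or moved by no more than one grade. On-treatment monitoring also limits the consequence, with biochemistry weekly in Cycles 1 and 2 (Section 7.6), although it does not repair the entry rule.

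**Conclusion.** Criterion 7 is wrong as written. A patient who fails either hepatic limit still meets it, and the protocol has no other numeric bilirubin, transaminase or ALP limit for entry. In logical terms, two of the four combinations are admitted that should not be, on the assumption that both limits were meant, as the lead-in suggests. The patient values are illustrative, and the number of patients affected cannot be derived. Harm is plausible but not shown. The point changes no sample-size or power figure. It should be corrected because it is a safety criterion for a first-in-human combination and the repair is simple.

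**What to change.** Delete *Either* and *Or* from the two liver rows so that the bilirubin limit (not applied in Gilbert's disease) and the ALT/AST and ALP limit are both required. Keep the 5 x ULN allowance for liver metastases, and keep *Either*/*Or* in the renal rows. As an optional clarification, state whether both transaminases or only the one the site uses must be in range.

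Also state whether the corrected liver limits apply before each cycle and at restart, since Section 5.4.1 reuses the eligibility parameters there.

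**Cost.** No new test is needed. Some patients with a single abnormal liver result become ineligible. If the limits apply at restart, some holds could lengthen, and this has consequences. Section 5.4.1 says "The maximum unscheduled dose interruption period is two weeks" and withdraws patients not recovered to Grade 1 by then. Under Section 3.1.1 a drug-related interruption of more than 14 days in Cycle 1 is a dose-limiting toxicity. The restart rule should therefore be settled deliberately rather than follow unnoticed from the wording change. The numbers affected cannot be derived.
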